## 1.6 Study Rationale and Hypothesis

In summary, surgical resection is the only potentially curative treatment for patients with pancreatic cancer. Patients with BRPC have tumors in close contact with the vasculature but not to the extent that resection is prohibited. Nonetheless, retrospective studies have shown that immediate resection in these patients is associated with an increased risk of positive margins, and a margin positive resection does not improve survival over that of patients with unresectable disease. Moreover, even in those patients where a successful resection is achieved, there is a high rate of early metastatic progression suggesting that micrometastatic disease is often present at diagnosis. Therefore neoadjuvant therapy is likely to improve outcomes in patients with BRPC to increase the likelihood of achieving a margin negative resection, provide early control of occult micrometastatic disease, and select those patients without systemic progression who would benefit from surgical resection.

Superior survival outcomes have been demonstrated with FOLFIRINOX compared to gemcitabine in patients with metastatic disease. Our institutional prospective phase II trial demonstrated the tolerability and efficacy of modified FOLFIRINOX in patients with LAPC and MPC. Prolonged progression free survival and overall survival were seen in patients with BRPC and LAPC, and R0 resections were achieved in 42% of patients. In addition, retrospective and phase II studies have documented the tolerability of stereotactic body radiation therapy (SBRT) in LAPC and the potential for improved local control. Contact between the tumor and neighboring vasculature complicates or prohibits resection in the setting of BRPC, and therefore local therapy to potentially reduce the degree of contact may be of benefit. Given the superior outcomes with FOLFIRINOX and the potential for improved local response with SBRT, we propose to evaluate the efficacy of pre-operative modified FOLFIRINOX followed by SBRT in patients with borderline resectable pancreatic adenocarcinoma. We hypothesize that pre-operative modified FOLFIRINOX followed by SBRT will improve the rate of R0 resections compared to historical controls treated with standard gemcitabine-based chemotherapy and fractionated radiation prior to surgery.

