### 2.2 Secondary Objectives

- 2.2.1 To evaluate the radiographic response to neoadjuvant therapy by comparing IV contrast CT scans before and after therapy.
- 2.2.2 To evaluate the pathologic response to neoadjuvant chemotherapy and stereotactic radiation.
- 2.2.3 To determine rates of recurrence (local only, systemic only, and both local and systemic), progression free survival, and overall survival.
- 2.2.4 To determine rates of grade 3 or greater gastrointestinal toxicity, including acute toxicities occurring within 3 months of treatment, and late toxicities occurring over 3 months after completion of radiation.

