## 5. ELIGIBILITY CRITERIA

### 5.1 Disease Characteristics

- 5.1.1 Histologically confirmed pancreatic adenocarcinoma
- 5.1.2 Borderline resectable pancreatic adenocarcinoma, determined centrally by review of a diagnostic CT scan and/or MRI scan with contrast by a dedicated surgical oncologist and radiologist, or as determined by EUS, and defined according to one of the following four NCCN consensus guidelines:
  - Tumors of the pancreatic head or uncinate process with:
    - Solid tumor contact with the common hepatic artery (CHA) without extension to the celiac axis (CA) or hepatic artery bifurcation allowing for safe and complete resection and reconstruction, or
    - Solid tumor contact with the superior mesenteric artery (SMA) of ≤180 degrees, or
    - Presence of variant arterial anatomy such that the degree of tumor contact affects surgical planning
  - Tumors of the pancreatic body or tail with:
    - Solid tumor contact with the CA of ≤180 degrees, or
    - Solid tumor contact with the CA of >180 degrees without involvement of the aorta and with intact and uninvolved gastroduodenal artery
  - Solid tumor contact with the superior mesenteric vein (SMV) or portal vein (PV) of >180 degrees, or contact of ≤180 degrees with contour irregularity of the vein or thrombosis of the vein but with suitable vessel proximal and distal to the site of involvement allowing for safe and complete resection and vein reconstruction
  - Solid tumor contact with the inferior vena cava (IVC)
- 5.1.3 No evidence of extrapancreatic disease on diagnostic imaging (CT, MRI, or PET scan), or laparoscopy, including nodal involvement beyond the peripancreatic tissues and/or distant metastases
- 5.1.4 No evidence of invasion into the duodenum or stomach, as determined by EGD/EUS

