## 9. CRITERIA FOR RESPONSE AND PROGRESSION

Response to treatment will be assessed by the treating physicians and investigators according to RECIST version 1.1, as follows:

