### **9.4 Evaluation of Best Overall Response**

In general, the patient's best response assignment will depend on the achievement of both measurement and confirmation criteria as outlined below and summarized in Table 1:

*Complete Response (CR):* Disappearance of all target lesions. Any pathological lymph nodes (whether target or non-target) must have reduction in short axis to  $< 10$  mm.

*Partial Response (PR):* At least a 30% decrease in the sum of diameters of target lesions, taking as reference the baseline sum diameters.

**Progressive Disease (PD):** At least a 20% increase in the sum of diameters of target lesions, taking as reference the smallest sum on study (this includes the baseline sum if that is the smallest on study). In addition to the relative increase of 20%, the sum must also demonstrate an absolute increase of at least 5 mm. (Note: the appearance of one or more new lesions is also considered progression).

**Stable Disease (SD):** Neither sufficient shrinkage to qualify for PR nor sufficient increase to qualify for PD, taking as reference the smallest sum of diameters while on study.

Table 1: Response Assessment in Patients with Measurable Disease

TARGET LESIONS	NON-TARGET LESIONS	NEW LESIONS	OVERALL RESPONSE	BEST RESPONSE FOR THIS CATEGORY ALSO REQUIRES:
CR	CR	No	CR	≥4 weeks confirmation
CR PR	Non-CR/Non-PD	No	PR	≥4 weeks confirmation
	Non-PD	No	PR	
SD	Non-PD	No	SD	Documented at least once >6 wks from baseline
PD	Any	Yes or No	PD	
Any	PD	Yes or No	PD	No prior SD, PR, or CR
Any	Any	Yes	PD	

CR=complete response, PR=partial response, PD=progressive disease, SD=stable disease

Every effort should be made to document the objective progression even after discontinuation of treatment

Response duration will be measured from the time measurement criteria for CR/PR (whichever is first recorded) are first met until the first date that recurrent or PD is objectively documented.

Stable disease duration will be measured from the time of start of therapy until the criteria for progression are met, taking as reference the smallest measurements recorded since the treatment started.

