Secondary endpoints include radiographic response to neoadjuvant therapy, pathologic response to neoadjuvant therapy, rates of recurrence (local only, systemic only, and both local and systemic), progression free survival, overall survival, and rates of grade 3 or greater acute and late gastrointestinal toxicity. We will compare levels of KRAS mutation-associated circulating tumor DNA, CA19-9, and elastography measures with outcomes including R0 resection using logistic regression, and progression free survival and overall survival using proportional hazards regression. We will code IV contrast scans as binary and compare the before/after treatment within the same subject using the McNemar test for matched pairs. We have not powered this study for these secondary and exploratory measures. Future correlative biomarker studies will be studied using standard bioinformatics methods. Progression free survival, and overall survival will be estimated using Kaplan-Meier analysis. The Cox proportional hazards regression model will be used to determine if survival outcomes are associated with patient characteristics or treatment-related toxicities.

We anticipate accrual will be completed in two years based on the fact that approximately 40 resections for pancreatic adenocarcinoma are performed annually at Yale New Haven Hospital, of which around a third are for BRPC.

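### Radiographic response is tested only by McNemar on an unnamed binary scan coding; under RECIST or resectability coding that test does not estimate response, and no response proportion is planned

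*Combined protocol and SAP*

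**What the plan says.** Objective 2.2.1 reads: "To evaluate the radiographic response to neoadjuvant therapy by comparing IV contrast CT scans before and after therapy". Section 12 turns this into a single sentence of analysis: "We will code IV contrast scans as binary and compare the before/after treatment within the same subject using the McNemar test for matched pairs". It does not say what the binary variable is, which scan is the later one, who is in the denominator, or what significance level applies. Section 8 schedules three CTs after baseline: after cycle 3, after cycle 7, and before surgery. Section 12 also says that the secondary measures are not powered.

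Section 9 sets the response standard: "Response to treatment will be assessed by the treating physicians and investigators according to RECIST version 1.1". Partial response is defined in Section 9.4 as "At least a 30% decrease in the sum of diameters of target lesions, taking as reference the baseline sum diameters". Section 12 does not refer to Section 9 for this endpoint.

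Criterion 5.1.2 fixes the disease state at entry: "Borderline resectable pancreatic adenocarcinoma, determined centrally by review of a diagnostic CT scan and/or MRI scan with contrast", with EUS as an alternative route. Sections 18.1 and 18.2 use radiographic response only as something to correlate with ctDNA and elastography; they do not plan an estimate of it.

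**The concern.** McNemar compares how often a yes/no state is present at two times in the same patients. It needs a state that can be yes or no at both. The two codings the protocol itself suggests, RECIST response and resectability, do not have that property at baseline. The planned p-value would then say little more than that some patients responded.

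The quantity a reader wants is the response rate with its precision, and nothing commits the investigators to report it. The feature, the later scan and the denominator are all left open in an open-label, single-arm trial where response is judged by treating physicians and investigators. Those choices could be made after the scans have been read.

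**Working it through.** **Inputs.** N = 28, or 13 if the trial stops after stage 1 (Section 12). The documents give no rate, power or significance level for this endpoint, so there is no stated figure to reproduce. The responder counts below are illustrative.

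**1. The test.** Let b be the patients coded no before and yes after, and c those coded yes before and no after. Exact two-sided McNemar is p = 2 × P(X ≤ min(b, c)) with X ~ Binomial(b + c, 0.5), capped at 1. Concordant patients do not enter. With c = 0 and b = k this becomes p = 2 × 0.5^k.

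**2. RECIST coding.** CR and PR are judged against baseline, so the baseline scan has no response status and no real pair exists. If every baseline is entered as no, c = 0 by construction.

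**3. Resectability coding.** Criterion 5.1.2 requires borderline disease, so nearly every baseline is not resectable. The EUS route allows rare exceptions. Hence c is about 0.

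**4. Same count, different rates.** For k = 6, p = 2 × 0.5^6 = 0.031. Exact (Clopper-Pearson) limits are the 0.025 quantile of Beta(x, n − x + 1) and the 0.975 quantile of Beta(x + 1, n − x).

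| Responders / pairs | Proportion | Exact 95% CI | McNemar p |
|---|---|---|---|
| 6/28 | 21% | 8.3% to 41.0% | 0.031 |
| 6/20 | 30% | 11.9% to 54.3% | 0.031 |
| 6/12 | 50% | 21.1% to 78.9% | 0.031 |

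**5. Same number of pairs.** With 28 pairs, p does fall as k rises: 0.031 at k = 6, 0.002 at k = 10, 0.0001 at k = 14. So p carries some information about k, but it is not an estimate. At k = 1 it is 2 × 0.5 = 1, although with every baseline at no a single responder already shows that the rate is not zero.

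**6. Where McNemar works.** Criterion 5.1.2 admits "Solid tumor contact with the superior mesenteric vein (SMV) or portal vein (PV) of >180 degrees, or contact of ≤180 degrees" (the second with further vein conditions), so degree of SMV/PV contact can vary at entry. Section 1.6 gives a reason to study it: "local therapy to potentially reduce the degree of contact may be of benefit". Section 12 does not name this or any other feature.

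**7. Missing pairs.** Suppose the later scan is the post-SBRT re-evaluation of Section 6.3. Section 6.2 gives SBRT only to patients free of distant progression, so complete pairs leave out those who had it before SBRT. The failure rule in Section 12 covers R0 resection only. The documents give no reliable size for this loss. Two background figures in Section 1.3 can be used only as assumptions:

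- Retrospective borderline series: (160 − 125)/160 = 22%; 0.219 × 28 = 6.1, about 6 missing.
- mFOLFIRINOX and chemoradiation trial: 7/22 = 32%; 0.318 × 28 = 8.9, about 9 missing.

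Ten responders would then be 10/28 = 36% (19% to 56%) of all enrolled, 10/22 = 45% (24% to 68%) of pairs, or 10/19 = 53% (29% to 76%) of pairs. Under resectability coding McNemar gives 2 × 0.5^10 = 0.002 each time and cannot show the difference.

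**The case against.** **The plan adopts neither coding.** Section 12 mentions neither RECIST nor resectability, and objective 2.2.1 is a before/after question that McNemar suits if the feature can vary at baseline. This stands. A reader might infer that the planned test is invalid outright; the documents do not support that, because the misfit depends on the coding. But RECIST is the only response standard in the protocol, and no feature that would suit the test is named.

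**A 2×2 table contains proportions.** This also stands. A reader might infer that the trial could not report a response rate; it could. What is missing is the commitment: a defined response, a denominator and an interval.

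**The attrition figures are weak.** Correct. A reader might infer that a fifth to a third of patients would be lost, but the documents do not show it. Section 1.3 says that 125 of 160 completed pre-operative therapy, while Section 12 says that 125 received it and treats them as all who started. For the second trial, neither the timing nor the site of progression is given, and its counts (15 + 7 + 1 = 23) exceed 22. Many patients who progress on chemotherapy could also have a cycle 3 or cycle 7 scan, so their exclusion depends on which later scan is chosen.

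**The endpoint is secondary and unpowered.** True, and it limits the impact. It also favours an estimate with an interval over an unpowered p-value.

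**Conclusion.** The point holds as a mismatch between a stated method and its endpoint. Under RECIST or resectability coding, McNemar responds only to the number of responders and does not estimate response; rates from 21% to 50% can share p = 0.031. This rests on a baseline state that is absent or essentially constant, which follows from Section 9.4 and criterion 5.1.2, with a small allowance for the EUS route. That patients with distant progression before SBRT drop out of complete pairs follows from Section 6.2 if the post-SBRT scan is used; the size of that loss is unknown.

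A reader should not extend this to the trial's main conclusion. No decision rule uses the McNemar result, and the R0 analysis does not depend on it. The plan should be changed because the gap is real and the repair is cheap.

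**What to change.** In Section 12, replace the McNemar sentence as the main analysis of radiographic response:

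- **Estimate:** the proportion of all enrolled patients with RECIST 1.1 CR or PR on the post-SBRT, pre-operative scan versus baseline, with an exact 95% CI.
- **Non-responders:** patients with no such scan, and patients with PD on the cycle 3 or cycle 7 scan whatever a later scan shows. This is a proposal by analogy with the R0 failure rule, which does not itself cover this endpoint.
- **Non-measurable disease only:** eligibility does not require measurable disease, and Table 2 has no PR category. Count these patients as responders only if CR, and report how many there are.
- **Reporting:** tabulate CR, PR, SD, PD and no scan. State that responses are unconfirmed, a departure from the "≥4 weeks confirmation" in Table 1. Give the proportion among scanned patients as a sensitivity analysis.
- **McNemar:** keep it only as a supplementary test on a named feature that varies at baseline, for example SMV/PV contact ≤180 versus >180 degrees among patients with that contact, baseline versus post-SBRT scan, with the number of pairs reported.

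The cost is wording only, since the scans are already scheduled. The downside is a conservative estimate based on unconfirmed responses.

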### 6.1 Neoadjuvant mFOLFIRINOX

Patients will receive eight cycles of neoadjuvant mFOLFIRINOX – one cycle every two weeks (+/- 3 days). One cycle is defined as 14 days, and treatment will be initiated on day one of a two week cycle. The drugs will be dosed and administered as follows:

- Oxaliplatin  $85 \text{ mg/m}^2$  IV infused over two hours, followed by
- Leucovorin  $400 \text{ mg/m}^2$  IV (or levoleucovorin  $200 \text{ mg/m}^2$  IV) over two hours
- Irinotecan  $135 \text{ mg/m}^2$  IV over 90 minutes (concurrent with leucovorin during the last 90 min of the leucovorin infusion)
- 5-FU  $300\text{mg/m}^2$  IV bolus, then  $2400 \text{ mg/m}^2$  continuous IV infusion over 46 hours

All patients will receive supportive care as follows:

- Pegfilgrastim (NeulastaTM) on day 3, 4, or 5.

- Anti-emetics including palonosetron or ondansetron, aprepitant, and dexamethasone, according to standard institutional protocols.
- Atropine is administered per standard guidelines for cholinergic symptoms during irinotecan infusion on day 1.
- Loperamide is administered per standard guidelines for chemotherapy-induced diarrhea.
- Patients will be counseled regarding potential side effects and their management.

Re-staging pancreas protocol CT scans will be performed after 3 and 7 cycles of mFOLFIRINOX. MRI can be substituted for patients unable to undergo a CT scan. A PET scan is optional if necessary for re-staging.

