#### **6.2.4 Treatment Delivery**

Linac-based SBRT will be delivered to a total dose of 33 Gy in 5 fractions over the course of 2 weeks, or maximum of 3 weeks (21 days). The fiducials will be contoured to aid in target localization. A cone beam CT (CBCT) will be obtained in the treatment position on the Linac prior to each treatment. The fiducials will be visualized on the day of treatment CBCT, and the patient position will be adjusted to align the fiducials to match that of the planning CT scan.

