#### **6.3 Surgery**

After completion of SBRT, patients will undergo re-evaluation for resection with a pancreas protocol CT scan, MRI if CT scan can not be tolerated, and PET or EUS if deemed necessary to determine resectability. Those patients who are determined to be potentially resectable will undergo a laparoscopy, followed by surgical resection within 4-12 weeks after completion of SBRT. For surgical resections occurring more than 12 weeks after SBRT, exceptions will be recorded and patients can remain on study with PI approval. Standard pathologic evaluation and staging will be performed.

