## 10. SUBJECT DISCONTINUATION

Patients will receive 8 cycles of neoadjuvant mFOLFIRINOX followed by SBRT, surgical resection, and post-operative mFOLFIRINOX to complete 12 cycles. Treatment will continue unless there is evidence of disease progression, or unacceptable toxicity as specified in section 7.3 of the protocol. Any patients deemed unresectable at the time of surgery will be discontinued from study treatment.

Patients who complete the study treatment phase without disease progression will enter a post-study surveillance phase. They will undergo history, physical exam, measurement of weight, evaluation of performance status, and laboratory assessments (including CBC, serum chemistries, liver function tests, CA 19-9, CEA, and a research blood collection, as specified in the study calendar) at three month intervals for three years, then every six months for two years, then annually or until disease recurrence or death. Cross-sectional imaging with CT or MRI will be performed at 6 month intervals for three years, and then annually for two additional years or until disease recurrence. After five years, patients will be followed annually until death; surveillance imaging and lab assessments are optional after five years.

In addition, subjects who meet the following criteria should be discontinued from study treatment:

- Any grade 3 or 4 toxicity that does not resolve within 3 weeks of holding treatment.
- Unwillingness or inability of subject to comply with study requirements
- Determination by the investigator that it is no longer safe for the subject to continue therapy, or that the constraints of this protocol are detrimental to the patient's health
- The patient no longer wishes to continue protocol therapy

All subjects will be followed for survival.

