### **13. ADVERSE EVENTS ANALYSIS, DEFINITION, AND REPORTING**

#### **13.1 Safety Analysis**

Safety will be analyzed for patients treated in this study.

At each visit, a brief focused history will be obtained and any indication of treatment related toxicity will be evaluated by appropriate examination and/or laboratory/radiographic studies.

Safety analyses will include summaries of adverse event rates and changes in laboratory results, as well as number of CTCAE toxicity grades for both laboratory and non-laboratory data.

The evaluation period should extend from date of first treatment until at least 30 days (or longer if so specified) from the last dose or until resolution from all acute toxicities associated with the drug administration.

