### **14.2 Duration of Reporting of SAEs**

From the date of first treatment until 30 days (unless otherwise specified) subsequent to last treatment or withdrawal of subject, new onset adverse events will be captured. Follow-up and reporting of these events will follow the same procedure as for AEs observed during the study period. In addition, any unexpected Serious Adverse Event that occurs more than 30 days after drug administration but is possibly, probably or definitely attributed to drug administration will be recorded and reported.

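### Section 12 relates PFS and OS to treatment-related toxicities by Cox regression without allowing for toxicities that start after time zero; ordinary ever/never coding would push the hazard ratio downward

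*Combined protocol and SAP*

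**What the plan says.** Section 12 plans Kaplan-Meier estimates of PFS and OS and then adds: "The Cox proportional hazards regression model will be used to determine if survival outcomes are associated with patient characteristics or treatment-related toxicities". It also says that the study is not powered for secondary and exploratory measures. It gives no time origin for PFS or OS, no coding for toxicity and no time-dependent covariate. The nearest time origin, start of therapy, is in Section 9.4 and applies only to the duration of stable disease.

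Toxicity accrues during follow-up. Section 13.1: "The evaluation period should extend from date of first treatment until at least 30 days (or longer if so specified) from the last dose". Section 14.2: "until 30 days (unless otherwise specified) subsequent to last treatment or withdrawal of subject, new onset adverse events will be captured". Section 2.2 includes "late toxicities occurring over 3 months after completion of radiation". Section 10 ties exposure to disease control: "Treatment will continue unless there is evidence of disease progression".

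**The concern.** A fixed covariate in a Cox model must be known at time zero. Treatment-related toxicity never is. A patient coded as having had a toxicity must have stayed event-free until it began, so that stretch of event-free time is credited to the toxicity group. A patient who progresses in month 2 has little chance to record a toxicity and counts against the no-toxicity group. Because treatment stops at progression, the protocol itself strengthens this link.

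The risk is a published statement that toxicity goes with longer survival when it does not, or that a harmful toxicity looks harmless. Baseline characteristics are not affected. The missing time zero adds little by itself, since Section 6 has treatment start within 14 days of registration.

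**Working it through.** **1. The plan's own figures.** Section 12 gives none for the Cox analysis. Its figures concern the R0 design. With stopping at 5 or fewer R0 resections among 13 and rejection at 15 or more of 28, exact binomial calculation gives power 0.9035 (stated 90%) and early stopping under the null 0.574 (stated 57%). The Cox model plays no part in them.

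**2. When toxicity can start (Sections 3.1, 6.1 to 6.4).**
- Neoadjuvant chemotherapy: 8 × 2 = 16 weeks, about 4 months.
- Longest full course on schedule: 16 + 4 (gap to SBRT) + 2 (SBRT) + 12 (to surgery) + 12 (to adjuvant start) + 8 (4 cycles) = 54 weeks, about 12 months.
- Late GI toxicity: 16 + 2 = 18 weeks plus 3 months, about month 7.1; with the permitted 4-week gap, about month 8. No minimum gap is stated, so this start is approximate.

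**3. How many patients fail inside those windows.** Under exponential survival the share failing by month *t* is 1 − 2^(−t/median). At an assumed median of 12 months it is 21% by month 4, 34% by month 7.1 and 50% by month 12. At 17.8 months (median PFS in the institutional trial in locally advanced disease, Section 1.4) it is 14%, 24% and 37%. Ever/never coding sends to the no-toxicity group anyone who fails before onset.

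**4. Simulation with true HR = 1.** Ever/never coding sets x = 1 if onset precedes the event or censoring time, for the whole of follow-up. Time-dependent coding sets x(t) = 1 only from onset.

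Inputs from the documents: n = 28; medians of 17.8 and 26.6 months (Section 1.4) and 18 months (Section 1.3); late GI rate 8% (Section 4.3). Assumed: the 12-month median; exponential survival; censoring uniform over 12-60 months; onset independent of survival; toxicity shares of 10-44%. Section 1.4 says only that grade 3-4 rates were reduced with the modified regimen. The top of the range equals the grade 3 or 4 neutropenia rate that Section 7.2.1 gives for oxaliplatin with 5-FU and leucovorin.

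| Endpoint and assumed onset | Share | Ever/never HR | False positives, n = 28 |
|---|---|---|---|
| PFS, front-loaded (exponential, mean 1 month) | 10-44% | 0.89-0.96 | 5-7% |
| PFS, uniform over months 0-4 | 10-44% | 0.80-0.90 | 5-8% |
| PFS, uniform over months 0-12 | 20% and 44% | 0.57-0.71 | 14-20% at 44% |
| OS, front-loaded, capture ends 1 month after progression | 20-44% | 0.96-0.98 | 5-7% |
| OS, uniform over months 0-4, same capture | 20-44% | 0.89-0.93 | 5-7% |
| Late GI, uniform over months 7.1-24 | 8% | 0.43-0.51 | 1-2% |

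The months 0-12 row converts mean log HRs of −0.57 to −0.34 in trials of 28, at medians of 12 and 17.8 months: exp(−0.57) = 0.57 and exp(−0.34) = 0.71. A separate run at a 30% share, medians of 10-26.6 months and follow-up cut at 60 months gave 0.66-0.78, with 6.9% false positives at median 18. The OS rows assume a median of 8 or 8.8 months after progression.

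**5. The same PFS and late-toxicity data, coded correctly.** Time-dependent coding gives HR 0.98-1.02. In trials of 28 its mean log HR is −0.02 to +0.08, and its root mean squared error ranges from at most about 0.05 higher than ever/never coding to clearly lower.

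**6. OS.** Where capture stops soon after progression, time-dependent coding still gives 0.92 (onset months 0-4, 44% share), against 0.89-0.90 for ever/never.

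**7. A truly harmful toxicity (HR 1.5, 30% share).** Ever/never coding gives 1.18-1.35 for onset in months 0-4 and 0.88-1.13 for months 0-12.

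**8. Late GI cases.** 28 × 0.08 = 2.2 if every patient stayed at risk. Counting only onset before event or censoring leaves 0.9-1.4 per trial, and none in 24-41% of trials.

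**The case against.** The plan does not prescribe ever/never coding. Cox regression accommodates time-dependent covariates, so the text permits the right analysis as well as the wrong one. That is correct, and a reader should not infer that the plan commits to the biased version. What remains is that one unqualified sentence covers baseline factors and toxicities alike and gives an analyst no reason to treat them differently.

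At n = 28 the bias is also modest against noise. For PFS with onset in the neoadjuvant months, the worst median bias in log HR is about −0.23 against a standard error of about 0.45, and false positives stay near nominal. This stands for early toxicity. It does not stand for onset across the whole course, which the schedule allows. Lack of power explains a wide interval; it does not remove a systematic shift.

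Three stronger readings are tempting and not supported:
- *The hazard ratio will be below 1.* The bias is downward. Whether the estimate falls below 1 depends on the true effect, as step 7 shows. Toxicity can also end protocol therapy (Sections 7.3 and 10) and so affect survival, which leaves the net direction in this trial unknown.
- *The bias is a halving of the hazard.* The 0.43-0.51 for late GI toxicity rests on about one case, and the Cox sentence does not name late toxicity.
- *The trial's conclusions are at risk.* No decision rule uses this model.

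**Conclusion.** The gap is real, and the remedy is a cheap improvement to an unpowered secondary or exploratory analysis. With no true effect, ever/never coding would give a hazard ratio of about 0.80-0.98 for toxicity arising in the neoadjuvant months, with false positives of 5-8%. It would give about 0.57-0.71 if toxicity through the adjuvant cycles is included, with false positives of 14-20% at a 44% share. A harmful effect would be understated. The direction follows from the coding. The size rests on the assumed toxicity share, onset pattern and exponential survival, and on onset being independent of survival. The R0 endpoint, the Simon decision and the safety rules are untouched.

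**What to change.** Add to Section 12, before any analysis of these data:

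*Time zero for PFS and OS is the first dose of study treatment. Each treatment-related toxicity enters the Cox model as a time-dependent covariate from its recorded onset date. Late GI toxicity is reported descriptively. Patient characteristics known at baseline are fixed covariates. For OS, some downward bias remains where toxicity capture stops soon after progression.*

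The cost is that onset dates must be recorded, the programming is slightly longer, and at low toxicity shares total error may be slightly larger. The change removes most of the bias for PFS; for OS the improvement is smaller (step 6), which is why the caveat belongs in the text.

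A fixed month-6 landmark for OS is an obvious alternative, but I would not prescribe it. SBRT ends at about weeks 18-23, so the 3-month acute window of Section 2.2 runs to about month 7.1-8.3 and a month-6 cut drops part of it. In simulation it also raised the root mean squared error of the log HR from 0.53-0.73 (ever/never) to 0.71-0.86.
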